2.1 Primary Objective

The primary objectives are to determine feasibility and the acute toxicity profile of accelerated partial breast radiation using protons.

2.2 Secondary Objectives

The secondary objectives of this study are to assess the late toxicities, cosmesis, and clinical efficacy of accelerated partial breast radiation using protons.

3 Subject Selection and Withdrawal

3.1 Inclusion Criteria

- Histologically confirmed diagnosis of invasive or non-invasive breast cancer.
- Invasive ductal, lobular, medullary, papillary, colloid (mucinous) or tubular histologies.
- AJCC T1 or T2; N0 or N1mic; Stage IA-IIA breast cancer or AJCC TIS (Stage 0) ductal carcinoma in situ without invasion
- Gross disease must be unifocal with pathologic (invasive and/or DCIS) tumor size 3 cm or less. (Patients with microscopic multifocality are eligible as long as total pathological size is 3 cm or less).
- Estrogen and/or progesterone receptor positive invasive breast cancer. DCIS stage 0 does not require receptor testing.

CONFIDENTIAL

This material is the property of the University of Pennsylvania. Do not disclose or use except as authorized in writing by the study sponsor

- No evidence of distant metastatic disease as documented by history and physical examination (radiographic staging only to be performed as indicated by symptoms or physical findings.)
- Patients must have an ECOG Performance Status of 0, 1 or 2
- Age ≥ 50 .
- Patients must be able to provide informed consent.
- Patients must have undergone breast-conserving surgery
- All tumors (invasive and non-invasive disease) must be excised with a minimum margin width of ≥ 2 mm. Re-excision of surgical margins is permitted. Focally close (<2 mm) or positive (tumor cells at the inked edge of the specimen) margins determined to be at an anatomic boundary of resection by the surgeon, such as posterior fascia for posterior margins or skin for anterior margins, are also acceptable.
- Patients with invasive breast cancer must be node-negative (N0) or have only microscopic disease (≤ 2 mm) in the nodes (N1mi). Patients with Stage IA – IIA are required to have axillary staging but it will not be done for patients with Stage 0 DCIS. Options for axillary staging include:
 1. Negative sentinel lymph node biopsy (SLNB)
 2. Level I-II axillary lymph node dissection (ALND) (6 or more nodes removed).
 3. Positive SLNB followed by completion ALND (6 or more nodes removed).
- Patients presenting with abnormal microcalcifications on a screening mammogram must have radiographically confirmed excision of the suspicious microcalcifications, either by specimen radiograph or post-biopsy mammograms.
- The patient must be enrolled on the study within 60 days following the last surgery for breast cancer (lumpectomy, re-excision of margins, or axillary staging procedure).
- The target lumpectomy cavity must be clearly delineated and the target lumpectomy cavity/whole breast reference volume must be $\leq 30\%$ based on the postoperative/pre-enrollment CT scan.
- Patients must have imaging (mammogram or breast MRI) of both breasts, unless opposite breast absent, within 6 months of diagnosis of their breast cancer. CBC/differential obtained within 6 months prior to registration on study, with adequate bone marrow function defined as follows: Absolute neutrophil count (ANC) $\geq 1,800$ cells/mm³; Platelets $\geq 75,000$ cells/mm³; Hemoglobin ≥ 8.0 g/dl (Note: The use of transfusion or other intervention to achieve Hgb ≥ 8.0 g/dl is acceptable).
- Patients with synchronous bilateral breast cancers who will be treated with radiotherapy to each breast are eligible, provided such treatment can be performed in a manner that avoids overlap between treatment fields. Both sides may be treated with APBI if the pathologic eligibility criteria are met for both tumors, or only one side may be treated with APBI if the criteria are met for only one tumor.
- Patients with a history of prior breast cancer in the opposite breast are eligible as long as treatment can be performed without overlapping any prior RT fields.
- Patients with a history of prior breast cancer in the ipsilateral breast treated with lumpectomy alone (no RT) are eligible as long as the other entry criteria for this study are met.
- Patients with a history of non-breast malignancies are eligible as long as they have not received prior radiotherapy to the thoracic region, and have a greater than 2 year interval without evidence of recurrence.

CONFIDENTIAL

This material is the property of the University of Pennsylvania. Do not disclose or use except as authorized in writing by the study sponsor

- Women of childbearing potential must be non-pregnant and non-lactating and willing to exercise an effective form of birth control during radiation therapy (e.g. oral contraceptive, IUD, condoms or other barrier methods etc.). Hysterectomy or menopause must be clinically documented.
- Patient must provide study-specific informed consent prior to study entry

3.2 Exclusion Criteria

- Male breast cancer
- T2 (>3 cm), T3, T4, Node positive (other than N1mi), or M1 disease
- Multifocal primary tumor.
- Clear delineation of the extent of the lumpectomy cavity is not possible.
- Prior or simultaneous malignancies within the past two years (other than carcinoma in situ of the cervix, CIS of the colon, melanoma in situ, thyroid cancer, and basal cell or squamous cell carcinoma of the skin).
- Any non-axillary sentinel node(s) positive. (Note that intramammary nodes are staged as axillary nodes).
- Patients who have had a positive SLNB but decline completion ALND are not eligible.
- Patients treated with neoadjuvant chemotherapy are not eligible.
- Palpable or radiographically suspicious ipsilateral or contralateral axillary, supraclavicular, infraclavicular, or internal mammary nodes, unless there is histological confirmation that these nodes are negative for tumor.
- Suspicious microcalcifications, densities, or palpable abnormalities (in the ipsilateral or contralateral breast) unless these were biopsied and found to be benign.
- Proven multicentric carcinoma (invasive cancer or DCIS) in more than one quadrant or two or more breast cancers not resectable through a single lumpectomy incision.
- Paget's disease of the nipple.
- Surgical margins that cannot be microscopically assessed or are positive at pathological evaluation. A focally positive margin determined to be at an anatomic boundary of resection by the surgeon, such as posterior fascia for posterior margins and skin for anterior margins, is also acceptable. If surgical margins are rendered free of disease by re-excision, the patient is eligible.
- Breast implants. (Patients who have implants removed are eligible).
- Prior ipsilateral breast or thoracic radiation for any condition.
- Collagen vascular disease, specifically dermatomyositis with a CPK level above normal or with an active skin rash, systemic lupus erythematosis, or scleroderma.
- Pregnant women, women planning to become pregnant and women that are nursing.
- Psychiatric or addictive disorders or other conditions that, in the opinion of the investigator, would preclude the patient from meeting the study requirements.
- Actively being treated on any other therapeutic research study.

3.3 Subject Recruitment and Screening

Subjects will be recruited from the Surgical, Radiation, and Medical Oncology practices at the Hospital of the University of Pennsylvania and from Network Sites of the University of

CONFIDENTIAL

This material is the property of the University of Pennsylvania. Do not disclose or use except as authorized in writing by the study sponsor

Pennsylvania Department of Radiation Oncology. The treating radiation oncologist will determine if the patient is a potential research candidate and has the capacity to consent. The treating radiation oncologist will approach and inform the patient about the study, thereby initiating the informed consent process. If the patient expresses interest in the study, the treating radiation oncologist will contact a qualified member of the research team in the Radiation Oncology department at the University of Pennsylvania and request availability for enrollment. Should slots be available, a qualified member of the research team will continue the formal consent process. This person will explain the requirements of the study and provide a copy of the Informed Consent Form. The person obtaining consent will state the volunteer nature of research and advise the subject to take sufficient time to discuss the study before making her decision to sign the informed consent document. If a decision to participate is made, the informed consent form is signed after which screening procedures will be performed. Patient eligibility will be evaluated based upon the criteria outlined in Section 3.1 and Section 3.2. After eligibility is established, a subject study number will be issued. Eligibility is confirmed with the study investigator. All members of the research team will have successfully completed patient oriented research training. **Subjects will receive all treatment in the Radiation Oncology Clinic of the University of Pennsylvania.** Subjects will not be paid for participating in the study. All medical costs will be the responsibility of the subjects and/or their insurers. Cost of living expenses will be the responsibility of the subjects.

At the Hospital of the University of Pennsylvania, we currently treat approximately 150 cases of stage 0-II breast cancer per year with radiation as a part of BCT. We anticipate that with the availability of proton radiotherapy, these numbers may increase. We estimate an annual accrual of 10-12 subjects per year. Following its approval by the IRB, this protocol will be listed on our website. Physicians within the Penn Radiation Oncology Network sites and our referring physicians will also be informed about the availability of this study.

3.3.1 Inclusion of Minorities

The University of Pennsylvania Cancer Center reports that minorities accounted for 14% of all patients (adult and pediatric) enrolled on therapeutic clinical trials. Furthermore, it is estimated that approximately 30% of cancer patients admitted to the Hospital of the University of Pennsylvania are minorities (Source: University of Pennsylvania Cancer Center Grant).

The University of Pennsylvania Cancer Center has developed a number of minority outreach strategies. These include development of relationships with local community organizations, presentations or distribution of materials to local groups regarding trials, advertisements in minority newspapers and magazines, and presentations to professional organizations. If under-accrual of minority subjects is determined to be a problem, we will employ these methods to improve accrual.

3.3.2 Vulnerable Populations

Children, pregnant women, fetuses, neonates or prisoners are not included in this research study.

CONFIDENTIAL

This material is the property of the University of Pennsylvania. Do not disclose or use except as authorized in writing by the study sponsor

3.4 Early Withdrawal of Subjects

3.4.1 When and How to Withdraw Subjects

- Recurrent or Progressive Disease: Subjects who have clinical or radiologic evidence of recurrent disease will undergo an evaluation to document the nature of the abnormality. If recurrent or progressive cancer is diagnosed, the subject will be considered off study at that time but all efforts will be made to follow patients for survival for as long as the patient chooses to be clinically followed.
- At the discretion of the Principal Investigator: Subjects may be withdrawn at any time during the study if the PI believes it is in the subject's best interest. In this event, the reasons for withdrawal will be documented.
- Treatment is interrupted for reasons of treatment-related toxicity for more than 5 days.
- Subject Participation: Refusal to continue treatment, follow-up, comply with the protocol or withdrawal of consent. In this event, the reasons for withdrawal will be documented.
- Any grade 4 toxicity thought to be definitely or probably caused by the treatment

Once the subject has discontinued treatment, the primary reason for discontinuing treatment must be clearly documented in the subject's records and on the CRF. The investigator will assess each subject for response at the time of withdrawal.

Every effort will be made to follow subjects off study for toxicity and survival. Acute toxicities will be assessed for 60 days from the last date of treatment. Survival will be followed for a minimum of 5 years.

4 Radiation Therapy

4.1 Treatment Planning, Imaging and Localization Requirements

All subjects will be immobilized on an angled breast board in the supine position. Patients may be positioned with alpha cradle casts, adjustable breast boards, wing boards, vac-loc, or other methods of immobilization at the discretion of the treating physician. All immobilization devices will be located outside of the treatment beam. Arms should be in an up position in order to eliminate CT scan artifacts from the humerus and be located outside of the treatment beam.

4.1.1 Radio-opaque markers may be placed on external landmarks at the time of CT for radiation planning at the direction of the treating physician.

4.1.2 A treatment planning 4DCT and /or breathold and free breathing scans in the treatment position will be required to define the clinical target volumes (CTV, iCTV) and planning target volumes (PTV). This CT must be post-lumpectomy. The CT should extend cephalad to start at or above the mandible and extend sufficiently caudally (or inferiorly) to the

CONFIDENTIAL

This material is the property of the University of Pennsylvania. Do not disclose or use except as authorized in writing by the study sponsor

inframammary fold to encompass the entire lung volume. A CT scan image thickness of \leq 0.3cm should be employed or as specified by the Proton Scanning Protocol. All CTs scans (freebreathing, 4D and breatholding) employed for dose calculation during the treatment planning process should be acquired without contrast. All scans which require contrast to define gross target volume (GTV) and clinical target volume (CTV) have to be acquired after the planning CT was obtained. All CT scans should be acquired with the subject in the same position and using the same immobilization device as for treatment. Treatment planning will be done using a 3D based CT treatment planning system. All tissues to be irradiated must be included in the CT scan. Based on the 4DCT evaluation an active motion management should be employed for target motion $> 1\text{cm}$ for passive scattering proton techniques or as indicated by the planning protocol for pencil beam scanning techniques. Treatment planning will be performed on the average CT data set or breathold CT data set.

4.1.3 External skin localizing marks, which may include permanent tattoos, are recommended for radiation daily localization and set-up accuracy.

4.2 Target Contouring

Target contouring follows the general guidliness enclosed bellow for breathold based delivery. For 4DCT all target structures will be derived based on the target motion during the breathing cycle (inhale, exhale phase) on the average CT.

4.2.1 The Gross Tumor Volume (GTV) is defined as the boolean volumetric combination of the seroma (radiographic abnormality seen in the breast corresponding with fluid and/or scar tissue in the lumpectomy cavity) and surgical clips (or other fiducial markers) as determined from CT, MRI, and other relevant clinical information.

4.2.2 The Clinical Target Volume (CTV) is defined as the GTV with a margin of 15 mm to account for microscopic disease extension of disease. However, the CTV will be limited to 5 mm from the skin surface and limited posteriorly at the boundary of the breast tissue extent at the pectoral muscle (chest wall and pectoralis muscles are not to be included).

4.2.3 The Planning Target Volume (PTV), defined as a uniform 5 mm expansion around the CTV, will provide a margin the CTV to compensate for set-up variability and target volume motion due to respiration.

4.2.4 The Evaluation Planning Target Volume (PTV_Eval) is equivalent to the PTV but excludes any part of the PTV that extends outside the patient, the first 5 mm of tissue under the skin surface, and any part of the PTV that extends beyond the posterior edge of the breast tissue (i.e., chest wall, pectoralis muscles, and lung are excluded). Clinical Target Volume (CTVinhale) is defined as the GTV inhale plus areas that are considered to contain potential microscopic disease on the inhale phase CT data set.

4.2.5 Clinical Target Volume (CTVexhale) is defined as the GTVexhale plus areas that are considered to contain potential microscopic disease on the exhale CT data set.

4.2.6 Imaged based CTV(iCTV) will be determined on the average CT data set as a boolean of the CTVinhale and CTVexhale of the target on the average CT data set. Alternatively it can be derived based on the 4D analysis of target motion or can be manually edited by the treating physician on the average CT data set based on the 4DCT data sets available.

4.2.7 The Planning Target Volume (PTV), defined as a uniform 5 mm expansion around the iCTV, will provide a margin the CTV to compensate for set-up variability and possible changes in target volume motion due to changes in respiration pattern.

4.3 Normal Structures

4.3.1 The dosimetrist will define two structures: Skin-2 (2 mm thick surface) and Skin-PTV (all PTVs subtracted from the surface contour). Skin-PTV is the normal tissue structure that is all tissue other than what is contoured as something else.

4.3.2 Organ at risk volume (OAR) is contoured as visualized on the planning CT or MR scan. Planning organ at risk volume (PAR) is the OAR volume expanded for setup uncertainty or organ motion. The physician will contour the OAR. The dosimetrist will create the PAR by expanding the OAR by 2-3 mm, depending on the situation.

4.3.3 The following normal structures will be contoured: skin, ipsilateral and contralateral whole breast reference volumes, thyroid, lung (right/left), heart and spinal cord.

4.4 Dose fractionation and specification

4.4.1 A total dose of 38.5 Gy (RBE) will be prescribed to the ICRU reference point (usually isocenter). Two fractions, each of 3.85 GY (RBE) separated by at least 6 hours, will be administered on 5 treatment days (over a period of 5 to 10 days) for a total of 10 fractions. A fractionation schedule of 3.85 Gy once a day for 10 fractions over 2-3 weeks is also permitted.

4.5 Treatment Planning

4.5.1 The dose will be prescribed to the ICRU reference point (usually the isocenter) to be consistent with the ongoing RTOG 04-13 study.

4.5.2 Dose constraints for PTV_Eval: 95% of the prescription dose should cover at least 95% of the PTV_Eval.

4.5.3 Dose Constraints for normal tissues:

- *Uninvolved normal breast:* Less than 60% of the whole breast reference volume should receive $\geq 50\%$ of the prescribed dose and $< 35\%$ of the whole breast reference volume should receive the prescribed dose.
- *Contralateral breast:* The contralateral breast reference volume, contoured using the same methods described for the ipsilateral breast reference volume, should receive $< 3\%$ of the prescribed dose to any point.
- *Ipsilateral lung:* $< 15\%$ of the lung can receive 30% of the prescribed dose.
- *Contralateral lung:* $< 15\%$ of the lung can receive 5% of the prescribed dose.

CONFIDENTIAL

This material is the property of the University of Pennsylvania. Do not disclose or use except as authorized in writing by the study sponsor

- *Heart (right-sided lesions):* < 5% of the heart should receive 5% of the prescribed dose.
- *Heart (left-sided lesions):* The volume of the heart receiving 5% of the prescribed dose (V5) should be less than the 40%.
- *Thyroid:* maximum point dose of 3% of the prescribed dose.

4.5.4 At least two fields should be employed for each treatment delivery. Preferably different sets of beam pairs should be employed for BID treatments in order to avoid skin toxicity. Plans should be carried out based on the departmental protocol.

4.5.5. Target coverage should be reviewed beam-by-beam based on the PTVeal, CTV, iCTV DVH indicators in order to ensure the robustness of the plan. Beam parameters should not be altered to reduce apparent “hot” or “cold” spots, or to increase conformality. The above criteria can be altered by the treating Physician in consultation with Physics.

4.6 Treatment Duration

Proton radiation therapy will, in most instances, be completed within 2 weeks of the start of treatment. This may be extended if subjects require a break from treatment. Criteria for break would include any **Grade 3 or Grade 4** toxicity. All subjects experiencing **Grade 4** toxicity will be taken off study. Further treatment plans will be decided at the discretion of their treating physician.

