7.1.3 Endpoints

Primary Endpoints

Feasibility will be based on multiple radiation planning and treatment parameters. Should a patient experience one of the following events, treatment will be deemed infeasible:

- a) Patient cannot be given treatment because anatomy is such that a dosimetrically satisfactory treatment plan cannot be devised. For example, the dosimetry is unsatisfactory if < 95% of the target volume is covered by 95% of the dose.
- b) Patient is unable to tolerate more than 20% of treatments using proton radiotherapy (i.e., >2 of the 10 fractions). This can be for any reason, including the inability to set the patient up within acceptable limits of tolerance, or the patient is unable to tolerate treatment position or immobilization for duration of treatment. Thus, up to 20% (i.e., 2 of the 10 fractions) of treatments could be delivered using photons.
- c) Patient is unable to complete all treatment within 5 days of the estimated date of treatment completion or requires a treatment break of \geq than 5 days.
- d) No more than 20% of patients experience an acute toxicity, as defined below.

Acute toxicity is defined as any grade 3 or higher hematologic or non-hematologic toxicity, including skin changes, as graded by the NCI CTC Version 5.0, observed **within 30 days from the end of radiotherapy**, which is probably or definitely related to proton therapy.

Secondary Endpoints

Late toxicity is defined as any grade 3 or higher hematologic or non-hematologic toxicity which occurs more than 30 days after end of therapy. Late toxicities will be graded according to the CTC Version 5.0. Special attention will be paid to fibrosis and cosmesis. The time frame for late toxicity is open-ended because late toxicities have been known to occur a year or more after therapy. Follow-up for late toxicity will cease when a patient experiences disease progression since 2nd line therapies may then be initiated.

Cosmesis will be scored using the Harvard scoring system (scale = excellent, good, fair, poor) and CTC Version 5.0. In addition, cosmesis will be scored by the cosmesis and breast pain subscales of the Breast Cancer Treatment Outcomes Scale (BCTOS) instrument.

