7.3 SAMPLE SIZE/POWER

Acute toxicity. A total of 57 patients will be enrolled and will contribute to the hypothesis test of the acute toxicity rate. Since these are favorable risk patients, no loss to follow-up by 30 days post-XRT is expected. With 57 patients, there is 90% power for a chi-square test at a 1-sided 10% significance level, to test the null hypothesis that the acute toxicity rate is $\geq 35\%$ (clearly unacceptable) versus the alternative hypothesis that the acute toxicity rate is $\leq 20\%$. This analysis will be performed when 57 patients have 30 day post-XRT data.

Cosmesis at 2 years. The rate of excellent to good cosmesis on the Harvard scale will be scored at 2 years post-XRT. We anticipate that 3 patients will enroll on the study with fair cosmesis at baseline and they will be excluded from this endpoint. In addition, we anticipate that another 4 patients will be lost or have progressive disease before 2 years and who are not scored as fair or poor cosmesis (i.e., considered a failure) at a time point prior to 2 years and they will be excluded from this endpoint. Thus 50 patients will contribute to the analysis of whether excellent to good cosmesis is maintained at 2 years post-XRT. With 50 patients, there is 90% power for a chi-square test at a 1-sided 10% significance level, to test the null hypothesis that the cosmesis rate is $\leq 70\%$ (clearly unacceptable) versus the alternative hypothesis that the cosmesis rate is $\geq 85\%$.

7.4 TRIAL DURATION.

A total of 57 patients will be enrolled. With an expected monthly accrual of 2 patients, this study will enroll for approximately 2.5 years and the total duration of the study is approximately 4.5 years, in order to follow patients for 2 year cosmesis.

8 Safety and Adverse Events

The principal and secondary investigators will be responsible for detecting, documenting and reporting all events that meet the definition of an AE or SAE as defined in this protocol.

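### Patients taken off study for toxicity have no stated cosmesis follow-up and no rule in the primary 2-year cosmesis analysis

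*Combined protocol and SAP*

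**What the plan says.** Two sections remove patients because of toxicity.

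- Section 4.6 (Treatment Duration): every subject with Grade 4 "toxicity will be taken off study. Further treatment plans will be decided at the discretion of their treating physician". No attribution to treatment is required.
- Section 3.4.1 (When and How to Withdraw Subjects) lists "Any grade 4 toxicity thought to be definitely or probably caused by the treatment" and, separately, "Treatment is interrupted for reasons of treatment-related toxicity for more than 5 days".

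Section 3.4.1 then says what continues: "Every effort will be made to follow subjects off study for toxicity and survival". Two windows follow. One is "Acute toxicities will be assessed for 60 days from the last date of treatment"; the other is a minimum of 5 years for survival. No window or visit schedule is given for late toxicity off study, and neither the Harvard score nor BCTOS is mentioned.

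Section 7.1.3 treats late toxicity separately: "The time frame for late toxicity is open-ended because late toxicities have been known to occur a year or more after therapy". The only stop it names is progression: "Follow-up for late toxicity will cease when a patient experiences disease progression since 2nd line therapies may then be initiated".

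Section 7.2.1 makes maintained excellent-to-good cosmesis at 2 years one of two primary phase II objectives. Section 7.3 reaches 50 evaluable patients by removing 3 with fair cosmesis at baseline and expecting that "another 4 patients will be lost or have progressive disease before 2 years". A patient already scored fair or poor before 2 years is kept as a failure. Removal for toxicity is not mentioned.

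**The concern.** Neither section separates the end of protocol treatment from the end of assessment. Read as written, a patient who leaves because of treatment harm is no longer scheduled for Harvard scoring, and the analysis section has no place for her. If she had no fair or poor score before leaving, the natural outcome is that she is excluded along with those lost or progressed.

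That exclusion is triggered by an effect of the treatment under test. If removed patients have worse cosmesis than the rest, the observed 2-year rate is too high and the test against 70% is too easily passed. Section 8.1 lists breast fibrosis that harms cosmesis among the possible late effects, so a link between serious breast toxicity and the cosmetic result is plausible. A score not taken at the visit cannot be recovered later.

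A smaller problem sits beside this one. Sections 3.4.1 and 4.6 disagree on whether a Grade 4 event must be attributed to treatment before the patient is removed, so the set of affected patients is not defined.

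**Working it through.** **Inputs (section 7.3):** n = 50 evaluable (57 − 3 − 4), null rate 0.70, alternative 0.85, one-sided 10% level (z = 1.2816), stated power 90%.

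**1. The plan's own figure.** The power of a one-sample chi-square test in its normal form is

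Φ[(|p1 − p0|√n − z√(p0·q0)) / √(p1·q1)]

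= Φ[(0.15 × 7.071 − 1.2816 × 0.4583) / 0.3571] = Φ(1.326) = 0.908.

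The stated 90% reproduces.

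**2. The cut-off.** At n = 50, 40 successes give z = (0.80 − 0.70)/√(0.21/50) = 1.54 and pass; 39 give 1.23 and do not. The exact chance of 40 or more at a true 70% is 0.079. The same rule gives cut-offs of 39, 38 and 37 at n = 49, 48 and 47.

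**3. Worst-case illustration.** The documents give no rate of removal for toxicity, so the number removed, k, is an assumption. Suppose 50 patients should be analysed and 35 successes are expected (70%, the null). Suppose k are dropped, all of whom would have been fair or poor and none of whom was so scored earlier. The rate among those left is 35/(50 − k), and the success probability is the binomial tail at the cut-off for that n. The fair comparison is uninformative loss at the same n with the rate still 0.70, because the discrete cut-off alone moves the figure.

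| k removed | n | cut-off | rate among those left | success probability, all removed would fail | success probability, uninformative loss |
|---|---|---|---|---|---|
| 0 | 50 | 40 | 70.0% | 0.079 | 0.079 |
| 1 | 49 | 39 | 71.4% | 0.133 | 0.092 |
| 2 | 48 | 38 | 72.9% | 0.211 | 0.107 |
| 3 | 47 | 37 | 74.5% | 0.316 | 0.124 |

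The excess due to informative removal is 0.133 − 0.092 = 0.041, 0.211 − 0.107 = 0.104 and 0.316 − 0.124 = 0.192.

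**4. Less extreme assumptions.** Let each patient be removed with probability q, and let a fraction f of removed patients be fair or poor. Holding the overall rate at 70%, the rate among those kept is (0.70 − q(1 − f))/(1 − q). For q = 0.05 and f = 0.6 this is 0.68/0.95 = 71.6%. Averaging over the number removed gives these success probabilities:

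| q | f = 0.3 (average risk) | f = 0.6 | f = 1.0 |
|---|---|---|---|
| 2% | 0.092 | 0.108 | 0.132 |
| 5% | 0.101 | 0.149 | 0.235 |
| 10% | 0.102 | 0.216 | 0.460 |

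At f = 0.3 the figures are no higher than uninformative loss produces. The bias appears only if removed patients are worse than average.

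**The case against.** A reader might infer that these patients are followed only for acute toxicity and survival, and so drop out of late toxicity as well as cosmesis. The documents do not support that. Section 3.4.1 says toxicity without restriction, and its 60-day limit applies to acute toxicity alone. Section 7.1.3 leaves late toxicity open-ended and ends it only at progression. A Grade 4 event after day 30 is itself Grade 3 or higher late toxicity and is already counted. What remains is that no off-study schedule for late toxicity is given.

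A reader might also infer that these are the patients most likely to have poor cosmesis. Section 1.7 points the other way: in an earlier proton series, severe acute skin toxicity did not appear to lead to poor cosmetic results. That series had 20 patients and a median follow-up of 12 months, and it does not speak to late Grade 4 breast injury. The direction is therefore open.

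The loss of cosmesis data is inferred from silence. Section 7.1.3 asks for attention to cosmesis in its late-toxicity paragraph and scores cosmesis partly by CTC, so off-study toxicity follow-up could pick up some of it. But section 7.3 tests the Harvard scale, which is not named for off-study patients. Fair or poor scores before removal are safe, because 7.3 counts them as failures.

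The triggers may also fire rarely. Treatment is mostly finished within 2 weeks, whereas the skin reactions in the earlier series were reported at 3 to 4 and 6 to 8 weeks. The other proton trial in section 1.7, with 50 patients, reported no acute toxicity above grade 2. Section 4.6 concerns the treatment period and may not be meant for later events, although 3.4.1 sets no time limit. All of this limits the size of the problem. It does not supply the missing rule.

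**Conclusion.** The point holds for the 2-year cosmesis analysis. The plan takes patients off study for treatment harm, does not name Harvard scoring or BCTOS among what continues, and has no rule for these patients in section 7.3. The 2-year rate is biased upward if their cosmesis is worse than average, and not otherwise. A downward bias in late toxicity is not shown.

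The size is unknown because the documents give no removal rate, and it may be small. One removed patient who would have failed adds about 4 percentage points to the chance of a false success; three add about 19. These are worst cases: every removed patient is assumed to fail, and none to have been scored fair or poor beforehand.

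The difference between 3.4.1 and 4.6 on Grade 4 attribution is a plain inconsistency and does not depend on any of these assumptions. Overall this is a cheap improvement rather than a flaw that undermines the design.

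**What to change.** - **Sections 3.4.1 and 4.6:** state that removal for toxicity or for a toxicity interruption ends protocol treatment only. The section 6.4 assessments (toxicity, Harvard cosmesis, BCTOS) then continue to 5 years unless the patient withdraws consent. This concerns data collection and leaves the treatment decision where it is.
- **Section 7.3:** include these patients in the 2-year cosmesis analysis with their observed scores. Add a sensitivity analysis that counts a missing 2-year score after toxicity removal as a failure. Making that the primary rule would be harder to defend: section 4.6 has no attribution condition, so an unrelated Grade 4 event could become a cosmesis failure.
- **Grade 4 trigger:** reconcile sections 3.4.1 and 4.6 on whether attribution to treatment is required.

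The cost is protocol wording. Section 6.4 already schedules these visits for patients on study. The cosmesis rate may look slightly less favourable.
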